During the course of this award, three CFC layups will be explored. The different layups were chosen after review of manufacturing techniques at Orthotic & Prosthetic Design prior to the award, review of existing literature, review of prior modeling results from our group, and through conversations with the CFC manufacturer. The goal of exploring the three layup schemes was to find the layup that 1) maximized deflection of the brace (i.e. indirect measure of energy return), while simultaneously 2) minimized stress within the brace (i.e. indirect measure of propensity for strut fracture and failure). The three CFC were each modeled with the same geometry (equal length and thickness), boundary conditions, and loading conditions.

Layup A: Unidirectional fibers, two out of every three layers were oriented along the longitudinal direction while the third layer was oriented in the transverse direction. This pattern was repeated

throughout the layup. The 2x2 twill was used on the very top and bottom layers rotated at a 45 degree angle from the principle axis. (Expectation: Greater strength along longitudinal axis with some strengthening in the transverse direction)

Layup B: 2x2 carbon twill without any rotation between layers. Half the fibers were along the principle axis and the other half 90 degrees to the principle axis. The cross section of this layup had the same strength in the longitudinal direction as it did in the transverse. (Expectation: Strength in both the longitudinal and transverse direction)

Layup C: Unidirectional fibers all in the same direction along the principle axis, meaning all of the fiber strength was oriented in the longitudinal direction. (Expectation: Strength along the principal axis only, no fibers in the transverse direction).

In order to test the results of the FE model, we will create a new brace for the study team member and we will enroll 10 individuals who currently have a Gillette ankle foot orthosis and foot complication related to diabetes. Participants will attend an initial study visit when they will sign a consent and have a mold of their foot taken in order to design carbon fiber off loading brace.

Participant selection, Inclusion and Exclusion Criteria

Inclusion Criteria

1. Daily life includes a minimum of moderate activity level (variable cadence walking)
2. Have a Gillette or carbon off loading orthosis as a result of diabetes related foot impairments

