3. Diagnosis of diabetes mellitus and peripheral neuropathy
4. Ability to ambulate in the community (K-level ≥ 2)
5. Age > 21 years

Exclusion Criteria (Must be a no)

1. Unable to ambulate and complete testing required for study participation.
2. Severe foot deformity of the hindfoot or any deformity of the foot with a dislocation resulting in a bony prominence on the plantar/weightbearing surface of the foot.
3. Neurological diseases that affects walking

Data Acquisition:

Participants who meet the inclusion/exclusion criteria will be identified by a member of the research team. A member of the research team will contact the participant to assess interest and schedule for testing. The first visit will begin with a member of the research team reading and explaining the informed consent document to the participant. After informed consent is obtained the research team member will create a mold of the participant's foot. The mold will be used in conjunction with the results from the FE model to create a new brace for the participant to be tested at a later date. The following tests will then be completed during the first visit:

- 1) Collection of medical and personal information: the participants will provide their and their doctor's contact information as well as medication list, a brief medical history, and information about activities of daily living.
- 2) Movement analysis: Reflective markers will be placed in various locations on the feet, legs, and body so we can record movements of the foot and leg while walking. We will place pressure sensing insoles into the participant's footwear to measure the amount of pressure when performing the activities listed during the recording. The participant will be recorded with the device or footwear while performing daily activities. The conditions under which they will walk with first will be randomized using a computer program which will generate a random order for the conditions. The recordings will be in a

format in which any information that identifies the participant is removed. The de-identified recording will be stored on a secure server, in a secured area behind locked doors. Only study personnel will have access to these computer files.

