- 3) Questionnaires: Foot and Ankle Ability Measure and Quebec User Evaluation of Satisfaction with Assistive technology 2.0 questionnaire (asks questions about use, comfort, effectiveness, and professional services). The participant is free to skip any questions that they prefer not to answer.
- 4) Plantar pressure testing: the participant will be asked to walk across a surface barefoot. This test will occur during one of the study visits and will take place at [name] in the Applied Kinesiology Lab.
- 5) Neuropathy Assessment: Foot sensation will be measured using a monofilament and a biothesiometer. Monofilaments are similar to fishing line of different thicknesses, and will be placed on the bottom of the foot to test if the participant feels it touching the skin. A biothesiometer is a vibrating wand that will be placed on the bottom of the foot to test if the participant feels it.

Following the first visit, a new CFO will be fabricated based on the mold and on results from a FE model. The participant will pick up the orthosis at the offices of Orthotic and Prosthetic Design. The orthosis will be examined and modified for comfort. The participant will then wear the brace from 1 week. If the brace is causing discomfort or pain during this week the participant may return to have it modified. The participant will return to O & P Design after a week. If necessary, the brace will be adjusted to avoid any rubbing on the foot or ankle. The participant will then continue to wear the orthosis and can return to O & P Design at any time to have the brace examined and modified for comfort. Once the participant has worn the brace for two consecutive weeks with no issue, they will return to complete tests 1-5.

Statistical Analyses:

A repeated measures ANOVA will be used to test for differences of the primary measure of peak plantar pressure at the forefoot, midfoot, and heel during walking while the participants are barefoot, wearing the CFO consistent with current clinical standards, and wearing the new CFO fabricated based on the results of the FE model. Statistical significance was set at $p < 0.05$.

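### Does testing the new orthosis only after two trouble-free weeks of wear, with no rule for participants who never get there, undermine the ANOVA?

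*Combined protocol and SAP*

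**What the plan says.** The brace-testing part of the study is small: "we will enroll 10 individuals who currently have a Gillette ankle foot orthosis and foot complication related to diabetes". First-visit tests take place before the new orthosis exists: "Following the first visit, a new CFO will be fabricated based on the mold and on results from a FE model". According to Data Acquisition, the brace is checked and adjusted at pick-up, can be modified during the first week, and is adjusted if necessary at the one-week return. After that the participant "can return to O & P Design at any time to have the brace examined and modified for comfort". The repeat tests follow only when a wear condition is met: "Once the participant has worn the brace for two consecutive weeks with no issue, they will return to complete tests 1-5". No deadline is given, and what counts as an issue is not defined.

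The Statistical Analyses section has two sentences. The first begins "A repeated measures ANOVA will be used to test for differences of the primary measure of peak plantar pressure at the forefoot, midfoot, and heel" and lists three within-person conditions: barefoot, standard CFO and new CFO. The second sets the 0.05 significance level. Neither defines an analysis set, a missing-data rule, or how participants not tested in the new brace are reported.

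**The concern.** Entry to the new-CFO measurement depends on how the participant got on with the new CFO, which is one of the conditions being compared. Someone who never has two trouble-free weeks contributes no new-CFO pressure. A conventional three-condition repeated measures ANOVA needs all three values per person, so that participant's first-visit data would be lost as well. If people who cannot wear the brace are also those whose pressures it lowers least, the new-versus-standard estimate would flatter the new design. The plan does not require the loss to be reported. With 10 people, even one such participant matters.

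**Working it through.** **Inputs from the documents.** Planned enrolment is 10 (Research Design and Methods). There are three within-person conditions and a 0.05 level (Statistical Analyses). The wear condition and unlimited adjustment come from Data Acquisition. The documents give no SD, expected effect, power or loss rate, so the 10 cannot be reproduced and there is no figure to correct. Everything below is assumed and shown as a range.

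**Step 1: chance of any loss.** If each participant independently has probability *p* of never meeting the condition, P(at least one of 10) = 1 − (1 − *p*)^10. This gives 40% for *p* = 5%, 65% for 10%, 89% for 20% and 97% for 30%. Losses are plausible if *p* is not small. The documents do not indicate *p*, and repeated refitting works to lower it.

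**Step 2: bias if there is loss.** Let the gap be the mean new-minus-standard difference in those lost minus that in those kept. The mean over all 10 is the kept mean plus (fraction lost × gap), so the completers' mean is off by fraction lost × gap.

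- No loss, or gap 0: bias 0.
- Gap 20 kPa, 1 of 10 lost: 0.1 × 20 = 2 kPa in favour of the new brace.
- Gap 60 kPa, 3 of 10 lost: 0.3 × 60 = 18 kPa in favour.
- Gap −20 kPa, 1 to 3 lost: 2 to 6 kPa against.

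The sign depends on a link between wear problems and plantar pressure that the documents do not give. The one specific wear problem they name is rubbing on the foot or ankle, which is not evidently a plantar peak-pressure problem. Every participant also has neuropathy ("Diagnosis of diabetes mellitus and peripheral neuropathy"), which may weaken any link between discomfort and pressure.

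**Step 3: effect on significance.** Simulated paired *t*-tests of new versus standard (kept mean −30 kPa, SD 35 kPa, 2 of 10 lost, 40,000 trials per row) give:

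| Gap (kPa) | p<0.05, completers | p<0.05, all 10 | True mean, all 10 (kPa) |
|---|---|---|---|
| −20 | 55% | 76% | −30 − 4 = −34 |
| 0 | 55% | 67% | −30 |
| 20 | 55% | 53% | −30 + 4 = −26 |
| 40 | 55% | 35% | −30 + 8 = −22 |
| 60 | 55% | 18% | −30 + 12 = −18 |

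The lower rows look alarming, but the true mean over all 10 favours the new brace in every row. With 3 lost and gap 60 it is still −30 + 18 = −12 kPa. A higher share of significant results is therefore not a false-positive rate here, and no row reverses the direction of the effect. The table also concerns one paired contrast; the planned ANOVA across three conditions was not simulated.

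**Step 4: precision.** For a paired contrast (two-sided 0.05), the standardized difference detectable with 80% power is 1.00 with 10 participants, 1.07 with 9, 1.16 with 8 and 1.27 with 7. Power at the 10-person value falls from 80% to about 75%, 68% and 60%. This is the ordinary cost of losing participants from a small study.

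**Step 5: would a worst-case analysis help?** One option is a signed-rank test that gives each lost participant the worst rank. With one of 10 lost and the other nine all favouring the new brace, the unfavourable rank sum is 10. Of the 1,024 sign patterns, 43 have a sum of 10 or less, so *p* = 2 × 43/1,024 = 0.084. With two lost (tied worst ranks), *p* = 0.42. The corresponding completer values are 2/512 = 0.0039 and 2/256 = 0.0078. After a single loss, no data could bring the bound below 0.05. It also treats a wear problem as the worst pressure result, which is the very link that is unknown.

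**The case for a change.** The strongest case for a change does not rest on the assumed kPa values. The wear condition is explicit, the plan itself expects fit problems, and no equivalent condition is stated for the standard brace. The plan does not say that its result applies to a tolerated brace, and one sentence plus a count of participants would settle this at almost no cost.

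Much of that stands. The text is silent, and a report should give the numbers enrolled, fitted and tested in the new brace, with reasons for any shortfall. But this asks for detail to be written down; it does not show that following the plan gives a wrong answer. The braces are made to test the finite element results, and pressure in a fitted, worn brace is the quantity that bears on this. Pressure in a brace that cannot be worn is not clearly defined. The comparison is also less lopsided than it looks: participants enter already having an off-loading orthosis, so the wear period brings the new device towards the same in-use state. Nor would a loss be invisible: an analysed number or ANOVA degrees of freedom short of the planned 10 would reveal it, though not the reason.

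**Conclusion.** The silence is real, but no change to the plan follows. Harm needs two things that the documents do not supply: participants who never meet the wear condition despite unlimited refitting, and a link between failing it and plantar pressure. Without the first there is no effect. With the first alone, only precision is lost. With both, the assumed range runs from 6 kPa against the new brace to 18 kPa in its favour, and the direction of the all-participant effect never reverses. That last statement rests on the assumed mean of −30 kPa among those kept.

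Stating the population and the participant flow is detail that a competent analyst would supply when reporting, using the number actually enrolled or fitted as denominator and a stated date for counting someone as not tested. A worst-rank analysis is a poor trade, because a single loss among 10 makes significance impossible. The wear, adjustment and testing rules are not in question here.

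### The primary analysis stops at an omnibus repeated measures ANOVA across barefoot, standard CFO and new CFO: it plans no new-versus-standard contrast and does not say how non-sphericity will be handled

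*Combined protocol and SAP*

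**What the plan says.** The Statistical Analyses section is two sentences. The first gives the method: "A repeated measures ANOVA will be used to test for differences of the primary measure of peak plantar pressure". The measure is taken in three regions of the foot. The conditions compared are "barefoot, wearing the CFO consistent with current clinical standards, and wearing the new CFO fabricated based on the results of the FE model". The second gives the threshold: "Statistical significance was set at $p < 0.05".

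The section has no sphericity test, degrees-of-freedom correction, covariance structure, planned contrast, post hoc rule or error term. It does not say that the ANOVA will be run without correction. It also does not say whether the three regions are analysed separately or as a second factor.

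The sample size stands just before the participant selection criteria: "we will enroll 10 individuals who currently have a Gillette ankle foot orthosis and foot complication related to diabetes". No SD, between-condition correlation, effect size or power figure appears anywhere.

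Under Data Acquisition, test 2 covers pressure in footwear: "We will place pressure sensing insoles into the participant's footwear to measure the amount of pressure". Test 4 is a separate procedure, in which "the participant will be asked to walk across a surface barefoot".

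**The concern.** The new brace is built to test the finite element results, so the comparison that answers the study question is new against standard CFO. The planned test asks something else: whether any of three conditions differs, one of them being no device at all. A significant result could come entirely from the barefoot condition.

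The same mixture of conditions makes sphericity doubtful. Sphericity requires the three pairwise differences to have equal variance. Two orthoses on the same foot may well track each other more closely than either tracks barefoot walking, which appears to be measured with a different set-up. If so, two things follow:

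- An uncorrected F test exceeds its stated level when all three means are equal.
- A follow-up comparison based on the pooled ANOVA error carries barefoot variability into the orthosis contrast and loses power.

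These act in opposite directions: the first makes the omnibus test liberal, the second makes the orthosis contrast conservative.

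**Working it through.** **Inputs from the documents:** 3 conditions, n = 10, alpha 0.05. **Assumed, because the documents give none:** SDs, correlations and effect sizes. Orthosis SD is set to 1, s is the barefoot SD, r_b the barefoot-orthosis correlation and r_o the correlation between orthoses. All 10 participants are taken as complete, with a one-way analysis per region.

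**1. The plan's own figure.** Error df = (3 − 1)(10 − 1) = 18 and the critical value is F(2, 18) = 3.5546. Under sphericity P(F > 3.5546) = 5.0%, so the stated level is reproduced.

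**2. The level if uncorrected.** Box's approximation is P(F(2ε, 18ε) > 3.5546), where ε runs from 1 (sphericity) to 0.5 (the minimum for three conditions).

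| ε | Type I error |
|---|---|
| 1.0 | 5.0% |
| 0.9 | 5.6% |
| 0.8 | 6.4% |
| 0.7 | 7.2% |
| 0.6 | 8.2% |
| 0.5 | 9.2% |

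Simulation (100,000 trials per covariance) agrees: 5.5% at ε = 0.91, 6.4% at ε = 0.76 and 9.0% at ε = 0.52. With Greenhouse-Geisser adjustment, simulated type I error was 4.1% to 5.2% over all covariances tried.

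**3. What a significant omnibus test means.** Set new equal to standard and shift only barefoot, by 1.5 barefoot SDs, with r_o = 0.7, r_b = 0.3 and s from 1 to 5. The omnibus F rejects in about 98% to 100% of trials. A second illustration, with a barefoot shift of 3 orthosis SDs over other covariances, gives 91% to 100%. These are correct rejections of the omnibus null, but they say nothing about the new brace.

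**4. The error term for new versus standard.** On average, the pooled error replaces the variance of the new-minus-standard difference by the mean of the three pairwise difference variances.

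- Orthosis difference: 2(1 − r_o). With r_o = 0.7 this is 0.6.
- Each barefoot difference: s² + 1 − 2·r_b·s. With r_b = 0.5 this is 1.0 for s = 1, and 2.25 + 1 − 1.5 = 1.75 for s = 1.5.
- Mean of the three: (0.6 + 1.0 + 1.0)/3 = 0.867 for s = 1, and (0.6 + 1.75 + 1.75)/3 = 1.367 for s = 1.5.
- Ratio to the correct 0.6: 1.44 and 2.28. The standard error is too large by factors of about 1.20 and 1.51.

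Simulated power for a new-versus-standard difference of 1 SD of the paired difference:

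| Covariance | ε | Paired error, 9 df | Pooled error, 18 df |
|---|---|---|---|
| s = 1, all correlations 0.5 | 1.00 | 80% | 85% |
| s = 1, r_b = 0.5, r_o = 0.7 | 0.91 | 80% | 73% |
| s = 1.5, r_b = 0.5, r_o = 0.7 | 0.76 | 80% | 52% |
| s = 2, r_b = 0.5, r_o = 0.8 | 0.60 | 80% | 13% |

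The pooled contrast's own type I error is 2.2% in the second row and 0.6% in the third. The paired test stays at 5.0% to 5.1% throughout.

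**The case against.** A reader might infer that the plan commits to an uncorrected test, that sphericity will be violated, and that the true level is therefore 6% to 9%. The documents support none of these three steps. Silence about a correction is not a decision against one. No SD or correlation is given, and mild departures (ε of 0.9 or more) leave the level at 5.0% to 5.6%, so 6% is not a floor.

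The premise of two closely similar orthoses is also open to doubt. The inclusion criteria admit users of either a Gillette or a carbon off-loading orthosis. The new brace has a different design, may be modified repeatedly, and is tested at a later visit. The barefoot test may share a visit with either device.

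The inflation also needs all three means to be equal, which is an unlikely null when off-loading devices are compared with barefoot walking. In addition, the plan names no contrast, so it cannot be said to use the wrong error term. The power loss depends on a choice that nobody has yet made, and its most extreme values need a barefoot SD several times the orthosis SD.

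All of this stands, and it makes the sphericity point on its own a modest one. It does not answer the main point: the test that is specified cannot separate a better brace from a barefoot effect, and the comparison that could do so is left open, error term included, until the data are in hand.

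**Conclusion.** The concern holds in a limited form. The stated analysis is an omnibus test that a barefoot difference alone can make significant, in about 98% to 100% of trials under the assumed shift of 1.5 barefoot SDs. The new-versus-standard comparison is not planned.

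If that comparison were later made with the pooled error, power for a difference of 1 SD of the paired difference could fall from about 80% to 73% or 52% under two moderate covariances, and lower if barefoot variance is larger. This is conditional on the pooled error being used.

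If the ANOVA is run uncorrected, its type I error lies somewhere between 5% and about 9%, and the excess matters only when all three means are equal. The documents do not allow a narrower statement.

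These figures apply to separate one-way analyses with 10 complete participants. If region were a second factor, the uncorrected interaction test (4 and 36 df) would have a different upper bound, 13.9% at ε = 0.25.

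**What to change.** Amend the Statistical Analyses section along these lines: *For each region, peak plantar pressure will be compared across the three conditions by repeated measures ANOVA with Greenhouse-Geisser adjusted degrees of freedom. New versus standard CFO is a planned contrast, tested with its own paired error (paired t test, 9 df with 10 complete participants) and reported with a 95% confidence interval.*

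This is a change of a sentence or two and needs no new data or participants. The omnibus test becomes slightly conservative (4.1% in simulation when sphericity holds). The paired contrast has 9 rather than 18 df, so it gives up a little power if sphericity does hold: about 80% against 85%. The correction alone would not be enough, because it does not change what the omnibus test asks. The planned contrast is the part that answers the device question.
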